1 INTRODUCTION AND OBJECTIVES OF ANALYSIS

1.1 Introduction

This document presents the statistical analysis plan (SAP) for Biohaven Pharmaceuticals, Protocol BHV3000-201: A Multicenter, Open Label Long-Term Safety Study of BHV-3000 in the Acute Treatment of Migraine.

This SAP is based on Version 6 of the BHV3000-201 protocol dated 20-DEC-2018. It contains the analysis details and methodology to answer the study objectives, including planned summary tables, by-subject listings, and figures, which will provide the basis for the results section of the clinical study report (CSR). Operational aspects related to collection and timing of planned clinical assessments are not repeated in this SAP unless relevant to the planned analyses.

1.2 Study Objectives

1.2.1 Primary Objectives

To evaluate the safety and tolerability of rimegepant.

1.2.2 Secondary Objectives

- To evaluate the frequency of elevations in Alanine Transaminase (ALT) or Aspartate Transaminase (AST) $> 3 \times$ the Upper Limit of Normal (ULN) with concurrent elevations in bilirubin $> 2 \times$ ULN in subjects treated with rimegepant.
- To evaluate the frequency and severity of hepatic-related adverse events (AEs) and the frequency of hepatic-related treatment discontinuations.

1.2.3 Exploratory Objectives

- To evaluate the frequency of subjects with elevated liver function tests (LFTs); AST, ALT or total bilirubin (TBL).
- To evaluate the frequency of subjects with ALT or AST elevations $> 3 \times$ ULN in temporal association with nausea, vomiting, anorexia, abdominal pain or fatigue.
- To explore the contributions of gender, age and exposure to rimegepant to abnormalities in AST, ALT, or bilirubin.
- To investigate the time on treatment and cumulative exposure associated with: (1) hepatic related serious AEs (SAEs) and treatment discontinuations; (2) elevations in ALT or AST $> 3 \times$ ULN with concurrent elevations in bilirubin $> 2 \times$ ULN.
- To evaluate the number of headache days and severity of migraine attacks while subjects are treated with rimegepant relative to the observational period (OP).

- To evaluate the effect of rimegepant treatment compared to baseline on the 20-Item Migraine-Specific Quality of Life Questionnaire (MSQoL) version 2.1.
- To evaluate the effect of rimegepant treatment compared to baseline on the Migraine Preference of Medication (PoM).
- To examine the scores on the Sheehan Suicidality Tracking Scale (S-STS).
- To evaluate the effect of rimegepant treatment compared to baseline on the Satisfaction with Medication (SM) Survey.
- To evaluate the effect of rimegepant treatment compared to baseline on the Migraine Disability Assessment (MIDAS).
- To evaluate the effect of rimegepant treatment compared to baseline on the Clinical Global Impression – Change (CGI-C) scale.

2 STUDY DESIGN

2.1 Synopsis of Study Design

BHV3000-201 is a Phase IIb, multicenter, open-label study designed to assess the safety and tolerability of long-term use of rimegepant, taken up to one tablet per calendar day, in patients with migraine.

The Screening phase includes a Screening Visit and a 30-day Observation Period (OP). For subjects to be eligible for the study, they must have 2-14 migraine attacks of moderate to severe intensity per month in the 3 months prior to the Screening Visit. Patients enrolled in the every other day (EOD) dosing group must have had 4-14 migraine attacks of moderate to severe intensity per month within the 3 months prior to the Screening Visit. Enrollment into this study will initially be open to patients with 2-8 moderate to severe migraine attacks per month (primarily the patients from BHV3000-301 and BHV-3000-302) for approximately 3 months. After approximately 3 months, study enrollment will open for patients with a history of 9-14 migraine attacks of moderate to severe intensity per month within the 3 months prior to the Screening Visit. Lastly, study enrollment will open for subjects (including patients from BHV3000-303) in the EOD dosing group (4-14 moderate to severe migraines per month).

After providing informed consent, patients will first participate in the Screening phase to determine eligibility for the study. At the Screening Visit, patients will be given an electronic diary (eDiary) to document on each day of the OP if a migraine occurred, intensity, and if it was treated. They will also be given a paper diary to record the standard of care migraine treatment.

After completing the OP, patients will return to the clinic for their Baseline Visit, where enrollment into the Long-Term Treatment (LTT) phase will commence and eligibility for continued participation in the study will be determined before study medication is dispensed. After the investigator reviews the results of the baseline laboratory assessments and determines continued eligibility, the site staff will inform the patient whether or not they are eligible to start

dosing in the Long-Term Treatment (LTT) phase in the 2-8 or 9-14 moderate to severe migraines/month group followed for 52 weeks, or the 4-14 moderate to severe migraines/month group followed for 12 weeks.

If in the 2-8 or 9-14 moderate to severe migraines/month group, patients will be instructed to take study medication at the onset of a migraine (of mild to severe intensity), with a maximum of one tablet per day. If in the 4-14 moderate to severe migraines/month group, patients will be instructed to take study medication every other calendar day, regardless of whether the patient has a migraine. However, they may take a tablet at the onset of a migraine (of mild to severe intensity), even if the migraine begins on a day they are not scheduled to dose.

Patients are required to record migraine occurrence and severity and all study medication doses in the eDiary and standard of care migraine treatment taken in the paper diary. Patients will also use the eDiary to complete the PoM and SM.

Study visits will be roughly every 2 weeks during the first month and then every 4 weeks until Week 52 (or Week 12 for patients in the EOD+PRN dosing group).

Patients will return to the study site at the end of Week 52 (or Week 12 for patients in the EOD+PRN dosing group) for the End of Treatment (EOT) Visit. There is also a Follow-Up Visit 14 days after the Week 12/Week 52/EOT Visit.

Protocol Version 5.0 was amended to Version 6.0 to re-open study enrollment in the 2-8 moderate to severe migraine attacks per month group to approximately 20 subjects at select sites in order to assess safety of rimegepant in combination with FDA-approved calcitonin gene-related peptide (CGRP) antagonist biologics (Aimovig™, Ajovy™, Emgality™). Patients at select sites with a history of 2-8 moderate to severe migraines/month taking a stable FDA-approved CGRP antagonist biologic will be instructed to take a maximum of one tablet per calendar day for 12 weeks to treat migraines of mild, moderate, or severe intensity. These subjects will follow the same study visit schedule as subjects in the 12-week EOD+PRN dosing group.

2.2 Randomization Methodology

There is no randomization in this open-label trial. Subject numbers, enrollment group, and study medication will be assigned via the Interactive Web Response System (IWRS). Note that enrollment group will be assigned at screening by IWRS based on migraine history in the 3 months prior to the Screening Visit (see Section 2.1).

Figure 1: Study Schematic (Up to 52 Weeks Treatment for 2-8 and 9-14 Moderate to Severe Migraines/Month Groups)

[figure not shown]
[figure not shown]

Figure 2: Study Schematic (Up to 12 Weeks Treatment for 4-14 Moderate to Severe Migraines/Month, EOD Dosing Group and Subjects Receiving FDA-Approved CGRP Antagonist Biologics in the 2-8 Moderate to Severe Migraines/Month Group)

2.3 Study Estimands

The tables that follow present the estimands corresponding to the study objectives.

Estimands are not adjusted for intercurrent events. Subjects that discontinue the study are tracked until they are no longer available.

2.3.1 Primary Estimands

The estimands corresponding to the primary endpoint for this study are shown in [Table 1](#).

Table 1: Estimands for the Primary Objective

Objective	Safety and Tolerability
Population	All treated subjects
Variables	Number and percentage of subjects with AEs occurring in $\geq 5\%$ of treated subjects by severity, SAEs, AEs leading to study drug discontinuation on treatment, and clinically significant laboratory abnormalities on treatment
Pop. Summary	Frequency by enrollment group and overall

2.3.2 Secondary Estimands

The estimands corresponding to the secondary objectives are shown in [Table 2](#).

Table 2: Estimands for the Secondary Objectives

Objective	Concurrent LFT elevations – Safety
Population	All treated subjects
Variables	Number and percentage of subjects with ALT or AST $> 3 \times$ ULN concurrent with TBL $> 2 \times$ ULN on treatment
Pop. Summary	Frequency by enrollment group and overall
Objective	Hepatic-related AEs – Safety
Population	All treated subjects
Variables	Number and percentage of subjects with hepatic-related AEs by severity, and hepatic-related AEs leading to study drug discontinuation on treatment
Pop. Summary	Frequency by enrollment group and overall

2.3.3 Exploratory Estimands

The estimands corresponding to the exploratory objectives are shown in [Table 3](#).

Table 3: Estimands for the Exploratory Objectives

Objective	LFT elevations – Safety
Population	All treated subjects
Variables	Number and percentage of subjects with LFT elevations (ALT, AST or TBL) on treatment
Pop. Summary	Frequency by enrollment group and overall
Objective	LFT elevations > 3 x ULN in temporal association with AEs – Safety
Population	All treated subjects
Variables	Number and percentage of subjects with ALT or AST > 3 x ULN concurrent with nausea, vomiting, anorexia, abdominal pain or fatigue on treatment
Pop. Summary	Frequency by enrollment group and overall
Objective	LFT abnormalities and elevations by subgroups – Safety
Population	All treated subjects
Variables	Number and percentage of subjects with LFT abnormalities and elevations on treatment by sex, age, exposure to rimegepant
Pop. Summary	Frequency by subgroup level
Objective	Hepatic-related AEs and concurrent LFT elevations by rimegepant exposure – Safety
Population	All treated subjects
Variables	Number and percentage of subjects with hepatic-related SAEs, hepatic-related AEs leading to study drug discontinuation, and ALT or AST > 3 x ULN concurrent with total bilirubin > 2 x ULN on treatment
Pop. Summary	Frequency by time on rimegepant, cumulative rimegepant exposure, and average rimegepant exposure
Objective	Migraine Days and Severity – Outcomes Research
Population	All treated subjects
Variables	Change from OP in the number of migraine days per 4 weeks during LTT(1) over time by 4-week intervals and (2) overall average, by severity (total; moderate or severe)
Pop. Summary	Change from OP by enrollment group and overall
Objective	Migraine-Specific Quality of Life (MSQoL) Questionnaire – Outcomes Research
Population	All treated subjects
Variable	Change from baseline in the MSQoL score over time for each dimension
Pop. Summary	Change in MSQoL score from baseline by enrollment group and overall at each post-baseline visit and the last post-baseline visit for each dimension

Table 3: Estimands for the Exploratory Objectives (Continued)

Objective	Preference of Medication (PoM) – Outcomes Research
Population	All treated subjects
Variable	Number and percentage of subjects in each of 5 preference categories (much better to much worse) of study medication relative to previous migraine medications over time
Pop. Summary	Frequency by enrollment group and overall at each post-baseline visit and last post-baseline visit
Objective	Sheehan-Suicidality Tracking Scale (S-STS) – Safety
Population	All treated subjects
Variable	Worst change from baseline in S-STS total score and subscale scores
Pop. Summary	Change from baseline to worst (highest) score on-treatment and follow-up by enrollment group and overall; number and percentage of subjects in each of 5 worst change from baseline score categories (< -1, -1, no change, 1, > 1) on-treatment and follow-up by enrollment group and overall
Objective	Satisfaction with Medication (SM) – Outcomes Research
Population	All treated subjects
Variable	Number and percentage of subjects in each of 7 satisfaction categories (completely satisfied to completely dissatisfied) of study medication over time
Pop. Summary	Frequency by enrollment group and overall at each post-baseline visit and last post-baseline visit
Objective	Migraine Disability Assessment (MIDAS) – Outcomes Research
Population	All treated subjects
Variable	Change from baseline in MIDAS scores over time
Pop. Summary	Change in MIDAS scores from baseline by enrollment group and overall at each post-baseline visit and last post-baseline visit
Objective	Clinical Global Impression - Change (CGI-C) – Outcomes Research
Population	All treated subjects
Variable	Number and percentage of subjects in each of 7 improvement categories (very much improved to very much worse) relative to investigator's past experience with other patients with the same diagnosis over time
Pop. Summary	Frequency by enrollment group and overall at each post-baseline visit and last post-baseline visit

3 POPULATIONS FOR ANALYSES

The following populations for analyses will be evaluated and used for presentation and analysis of the data:

- Screened subjects: Subjects who sign an informed consent form and are assigned a subject identification number and enrollment group by IWRS.
- Enrolled subjects: Screened subjects who have a non-missing enrollment date (i.e., enrolled in the LTT period).
- Treated subjects: Enrolled subjects who take any amount of rimegepant.
- Follow-up subjects: Treated subjects whose last contact date is in the follow-up safety analysis period (see Sections 5.3 and 5.4).

The number of subjects in each population will be presented by enrollment group and overall. A by-subject listing of populations for analyses will be provided for screened subjects.

4 STATISTICAL METHODS

4.1 Sample Size Justification

With a sample size of roughly 2000 subjects, and with no events observed, the upper bound of a one-sided, 95% confidence interval (CI) for zero observations is roughly 0.0015. Hence, this sample size is large enough to rule out AEs that occur at rates greater than 15 cases per 10,000 patients.

This study has a subpopulation of approximately 800 subjects with more frequent migraines that is expected to have a greater exposure to the study drug. With this sample size, and no events observed, the upper bound of a one-sided, 95% CI for zero observations is roughly 0.00375. Hence, this sample size is large enough to rule out AEs that occur at rates greater than 37.5 cases per 10,000 patients.

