**Number of Subjects:** 

Approximately 2800 patients will be screened to assign up to approximately 2000 patients to rimegepant.

Of the 2000 patients assigned to rimegepant, up to approximately:

- 1200 will have a history of 2-8 moderate to severe migraine attacks per month,
- 600 will have a history of 9-14 moderate to severe migraine attacks per month, and
- 200 will have a history of 4-14 moderate to severe migraine attacks per month in the every other day dosing group.

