#### 1.3.4 Clinical Adverse Event Profile

To date, 7 clinical studies have been completed in healthy volunteers and migraineurs that inform PK, metabolic interactions, safety, tolerability and efficacy. In total, the current data suggests a favorable benefit-risk profile for rimegepant in the acute treatment of migraine attacks. Efficacy was established in Study CN170003, and the overall database suggests a favorable safety profile. Clinical experience with rimegepant has also allowed the characterization of safety and tolerability at substantial multiples of the intended therapeutic exposure and intended frequency of use. Rimegepant has been assessed in single doses up to 1500 mg and in multiple doses from 75 mg to 600 mg with 14-days of dosing (including 300 mg twice daily), where the higher doses yielded exposures more than 60 times greater in AUC and 30 times higher in Cmax as compared to the mean therapeutic exposure of a single 75 mg dose. These high exposure multiples were generally well tolerated and safe.

Rimegepant appears to be generally safe and well tolerated in humans when given as single oral doses up to the maximum dose of 1500 mg and multiple oral doses up to the maximum daily dose of 600 mg for 14 days. Please refer to the Investigators Brochure for a summary of the clinical safety profile.

The primary identified AE of interest is potential change in liver function tests. Investigators must carefully monitor routine liver function tests (ALT, AST, total bilirubin, and ALP) and potentially liver related symptoms and signs. Clinicians should also monitor changes in hematology and other laboratory measures. Please refer to the current Investigators Brochure for further information regarding the clinical safety profile of rimegepant.

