## 9.2 Sample Size

With a sample size of roughly 2000 subjects, and with no events observed, the upper bound of a one-sided, 95% confidence interval for zero observations is roughly 0.0015. Hence, this sample size is large enough to rule out adverse events that occur at rates greater than 15 cases per 10,000 patients.

This study has a subpopulation of approximately 800 subjects with more frequent migraines that is expected to have a greater exposure to the study drug. With this sample size, and no events observed, the upper bound of a one-sided, 95% confidence interval for zero observations is roughly 0.00375. Hence, this sample size is large enough to rule out adverse events that occur at rates greater than 37.5 cases per 10,000 patients.

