#### 9.3.2 Secondary Endpoint(s)

The frequency of subjects that have confirmed values of ALT or AST that exceed 3x the ULN concurrently with confirmed total bilirubin that exceeds 2x the ULN will be tabulated and presented with descriptive statistics and exact confidence intervals.

Both hepatic related AEs and hepatic related AEs leading to discontinuation will be summarized in a manner similar to that described for the primary endpoint.

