4.6.2 Secondary Safety Endpoints

The following secondary endpoints will be summarized by enrollment group and overall: frequency of on-treatment elevations of AST or ALT $> 3 \times$ ULN concurrent with TBL $> 2 \times$ ULN; frequency and severity of on-treatment hepatic-related AEs; and frequency of on-treatment hepatic-related AEs leading to study drug discontinuation.

AST or ALT $> 3 \times$ ULN concurrent with TBL $> 2 \times$ ULN is defined as elevations on the same collection date, and will be summarized as the number and percentage of subjects experiencing these elevations concurrently on treatment and during follow-up. This will include two-sided Agresti-Coull 95% CIs for each percentage. These will be summarized together in the same table as other LFT elevation endpoints (see Section 4.6.3.1).

Refer to the BHV3000 Core SAP for hepatic-related AEs.

See also Section 4.8.2 for additional details about AEs, and a comprehensive list of AE tabulations.

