4.8.2 Adverse Events

Refer to the BHV3000 Core SAP for AE start date imputation, AE counting rules, definition of treatment-emergent adverse events (TEAEs), and definition of AEs related to study drug.

Tables will present the number and percentage of subjects experiencing AEs by SOC and PT, unless specified otherwise.

A by-subject listing of all AEs will be provided for screened subjects that will flag on-treatment and treatment-emergent AEs. Additional by-subject listings of deaths, SAEs, AEs leading to study drug discontinuation, hepatic-related AEs, and AEs of special interest (i.e., potential drug abuse, CV, and suicidality) will be provided for screened subjects. Refer to the BHV3000 Core SAP for listing content and AEs of special interest.

AE Overview

An AE overview without SOC and PT will present the number and percentage of subjects with any the following AEs: any AE; severe AE; AE related to study drug (unlikely related, possibly related, or related); SAE; SAE related to study drug; AE leading to study drug discontinuation; AE leading to death; hepatic-related AE; severe hepatic-related AE; hepatic-related SAE; hepatic-related AE leading to study drug discontinuation; potential drug abuse AE; CV AE; suicidality AE. An AE overview will be produced for each the following analysis periods and populations:

- Pre-treatment AEs for screened subjects by enrollment group and overall
- Pre-treatment AEs for treated subjects by enrollment group and overall
- TEAEs for treated subjects by enrollment group and overall
- On-treatment AEs for treated subjects by enrollment group and overall
- On-treatment AEs for treated subjects by subgroup level and overall for all subgroups of interest specified in Section 4.2.6
- Follow-up AEs for follow-up subjects by enrollment group and overall.

Pre-Treatment AEs

Pre-treatment AEs will be summarized by SOC and PT by enrollment group and overall for screened subjects for the following endpoints:

- AEs
- SAEs.

Pre-treatment AEs will be summarized by SOC and PT for treated subjects by enrollment group and overall for the following endpoints:

- AEs by severity (total, mild, moderate, severe, moderate or severe, not reported)
- SAEs.

On-Treatment AEs

On-treatment AEs will be summarized by SOC and PT for treated subjects by enrollment group and overall for the following endpoints:

- AEs by severity*
- TEAEs by severity

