6 CHANGES TO PLANNED ANALYSES IN THE PROTOCOL

There are no changes to planned analyses in the protocol at this time.

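### For ALT/AST elevation concurrent with bilirubin elevation, the SAP plans two-sided Agresti-Coull intervals where the supplied protocol says exact; at zero or few events these are needlessly wide and can go below zero

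*SAP*

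**What the plan says.** **Sample size.** SAP 4.1 and Protocol 9.2 give the same argument. With no events in roughly 2000 subjects, the one-sided 95% upper bound is about 0.0015, or 15 per 10,000. For a subpopulation of about 800, SAP 4.1 says "With this sample size, and no events observed, the upper bound of a one-sided, 95% CI for zero observations is roughly 0.00375", and Protocol 9.2 calls this "large enough to rule out adverse events that occur at rates greater than 37.5 cases per 10,000 patients".

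**Intervals in the SAP.** For the first secondary endpoint (ALT or AST above 3 times ULN on the same date as total bilirubin above 2 times ULN), SAP 4.6.2 says: "This will include two-sided Agresti-Coull 95% CIs for each percentage". SAP 4.6.3.1 repeats Agresti-Coull for this row and for a second row that adds an ALP condition. For adverse events, SAP 4.8.2 says "Tables will present the number and percentage of subjects experiencing AEs by SOC and PT, unless specified otherwise"; it states no interval.

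**Interval in the protocol.** Protocol 9.3.2 says that subjects with these concurrent elevations "will be tabulated and presented with descriptive statistics and exact confidence intervals". It gives neither the sidedness nor the level.

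**Declared changes.** SAP 6: "There are no changes to planned analyses in the protocol at this time".

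**The concern.** Protocol 1.3.4 states: "The primary identified AE of interest is potential change in liver function tests". The concurrent elevation is therefore the rate that readers of the study report will look at most closely, and zero is the count on which the sample size was argued. At zero or one event, interval methods for a proportion differ most in relative terms. Agresti-Coull is a normal approximation around a shifted estimate, so near zero its lower limit can be negative and its upper limit runs above the exact one. The plan thus appears to replace an exact method with an approximate one where the approximation does worst, and does not list the replacement as a change.

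There is also a loose end. The one-sided bound that carries the whole sample size argument appears in no planned table. If no concurrent elevation occurs, the design section will speak of 15 per 10,000, while the table prints a different and larger limit with nothing to connect the two.

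**Working it through.** **Inputs.** n = 2000 and 800 (SAP 4.1). Planned enrollment groups of 1200, 600 and 200 (Protocol synopsis and Section 5; the smallest is described as "200 will have a history of 4-14 moderate to severe migraine attacks per month in the every other day dosing group"). z = 1.960. All limits below are per 10,000.

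**Step 1: reproduce SAP 4.1.** The one-sided exact bound at zero events is 1 - 0.05^(1/n).
- n = 2000: 0.001497, or 14.97. The approximation 3/n gives 15.0.
- n = 800: 0.003738, or 37.4. The approximation 3/n gives 37.5.

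Both stated figures are right for the bound they name.

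**Step 2: two-sided exact (Clopper-Pearson) at zero events.** Upper limit = 1 - 0.025^(1/n). For n = 2000 this is 0.001843, or 18.4. Taking the protocol's exact interval as two-sided 95% is an assumption.

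**Step 3: planned Agresti-Coull.** With x events, n~ = n + z^2, p~ = (x + z^2/2)/n~, and the limits are p~ ± z·sqrt(p~(1 - p~)/n~).
- x = 0, n = 2000: n~ = 2003.84, p~ = 0.000959, half-width 0.001355. Limits -4.0 and 23.1.
- x = 1, n = 2000: p~ = 0.001458, half-width 0.001670. Limits -2.1 and 31.3. Clopper-Pearson gives 0.13 and 27.8.

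**Step 4: is the difference confined to zero and one event?** At n = 2000:

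| Events | Agresti-Coull | Clopper-Pearson |
|---|---|---|
| 0 | -4.0 to 23.1 | 0 to 18.4 |
| 1 | -2.1 to 31.3 | 0.13 to 27.8 |
| 2 | 0.2 to 38.9 | 1.2 to 36.1 |
| 3 | 2.9 to 46.2 | 3.1 to 43.8 |

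The exact interval is narrower at all four counts, and the difference remains if negative limits are cut at zero.

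**Step 5: the columns that will be printed.** SAP 4.2.1 tabulates three enrollment groups and overall. Upper limits at zero events:

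| Column | n | Agresti-Coull | Two-sided exact | One-sided exact |
|---|---|---|---|---|
| Overall | 2000 | 23.1 | 18.4 | 15.0 |
| PRN 2-8 | 1200 | 38.5 | 30.7 | 24.9 |
| PRN 9-14 | 600 | 76.7 | 61.3 | 49.8 |
| EOD+PRN | 200 | 226.9 | 182.8 | 148.7 |

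The 800 can only be 600 + 200, and no planned column pools those two groups.

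**Step 6: split the overall gap.** From 14.97 to 23.13 is 8.2. Moving from one side to two accounts for 18.43 - 14.97 = 3.5. Moving from exact to Agresti-Coull accounts for 23.13 - 18.43 = 4.7.

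**The case against.** The case for leaving the plan alone has real weight. Agresti-Coull is a recognised method, and the SAP also uses it for the PoM, SM and CGI-C percentages. For a liver signal, a higher upper limit errs on the cautious side. The study is single-arm with no test or decision rule, and moving from 27.8 to 31.3 per 10,000 at one event would change no clinical conclusion. The SAP does not say that a negative limit would be printed as such. A sizing statement need not reappear as a table cell.

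Most of that stands, and it limits the point to a modest one. It does not justify the choice, however. The extra width comes from the approximation and buys no assurance that the exact interval lacks, since Clopper-Pearson already guarantees at least 95% coverage. Cutting a negative limit to zero at one event would leave an interval that includes a zero rate after an event has been seen.

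Four stronger readings are tempting, and the documents do not support them:
- **That SAP 4.1 is miscalculated, or that more subjects are needed.** Its figures are correct for the one-sided bound it names, and it speaks of adverse events in general, for which this SAP states no interval. The choice of interval for two laboratory rows does not make the sample inadequate.
- **That the 37.5 claim will be contradicted by a printed limit.** No planned column holds those 800 subjects.
- **That returning to exact intervals would by itself restore 15 per 10,000.** Two-sided exact gives 18.4; only the one-sided bound gives 15.0.
- **That SAP 6 is shown to be wrong.** The SAP is based on protocol Version 6. The supplied protocol lacks the CGRP-biologic cohort that SAP 2.1 attributes to Version 6, so it appears to be earlier. The SAP's account of that amendment mentions no change of interval, but the departure has to be checked against Version 6.

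**Conclusion.** The point holds for the two concurrent ALT/AST and bilirubin rows. The planned Agresti-Coull interval differs from the exact interval in the supplied protocol and is the worse choice at the counts on which this study was planned. At 0/2000 its upper limit is 23.1 against 18.4 per 10,000; at 1/2000 it gives -2.1 to 31.3 against 0.13 to 27.8. Separately, the one-sided bound behind SAP 4.1 is correct but shown nowhere.

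This assumes the planned group sizes. SAP 4.6.3.1 counts only subjects with liver test data in the period, so actual denominators are likely to be somewhat lower and all limits somewhat higher. It also takes the protocol's exact interval as two-sided 95%. The BHV3000 Core SAP was not available, but SAP 4.6.2 names its interval directly. The undeclared change remains provisional until Version 6 is checked; the case for exact intervals in these rows does not depend on that check.

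**What to change.** 1. In SAP 4.6.2 and 4.6.3.1, specify Clopper-Pearson two-sided 95% intervals for the two concurrent rows, with and without the ALP condition. Agresti-Coull can stay for PoM, SM and CGI-C.
2. In the overall column of the same rows, also print the one-sided 95% exact upper bound. At 0/2000 it reads 15.0 per 10,000, so the overall claim in SAP 4.1 can be seen in the table.
3. Check the wording of Section 9.3.2 in protocol Version 6.
4. If Agresti-Coull is kept and Version 6 still says exact, list the change in SAP 6. In any case where it is kept, add to SAP 4.1 that the two-sided limit reported at zero events would be about 23 per 10,000 overall.

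The cost is one interval option, one added statistic in the liver test elevation tables, and a few lines of SAP text. No new data or subjects are needed.
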